**5.4.1.3. Distribution of percentages of serogroup B invasive disease strains killed**

Analysis set: FAS will be the primary analysis population. The ABCWY (pooled lots) group and the MenB group comparator that will be selected (ref: the footnote of [Figure 2](#)) will be used for the purpose of this analysis.

Statistical method: Summary statistics of the percentage of serogroup B invasive disease strains killed within a subject using enc-hSBA at 1 month after the 3-dose (0,2,6-months in MenB\_0\_2\_6 group) and 2-dose (0,6-months in MenB\_0\_6 group, 0,2-months in MenB\_0\_2\_6 group and 0,6-months in the ABCWY (pooled) group) vaccination series of rMenB+OMV NZ and MenACWY vaccines.

Summary statistics and 95% CI for the mean percentage will be presented, as well as a Figure of the cumulative distribution function.

#### 5.4.1.4. Immune response of MenABCWY, rMenB+OMV NZ and MenACWY

Analysis set: The analysis will be based on the FAS.

Statistical method: The hSBA titres at each time point for all groups (ABCWY group (pooled lots), MenB\_0\_2\_6 and MenB\_0\_6 groups) will be logarithmically transformed (base10) to fulfil the normal distribution assumption. For each *N. meningitidis* serogroup A, C, W and Y and each B indicator strain (M14459, 96217, M13520 and NZ98/254 for fHbp, NadA, NHBA and PorA P1.4 antigens, respectively), the GMTs and GMRs (post-vaccination/baseline) will be obtained from an Analysis of Variance (ANOVA) with factors for vaccine group, region (US/ex-US), age category (10-17 YoA/18-25 YoA), and previous MenACWY vaccination (y/n), and then exponentiating the log-transformed means and their 95% CIs. The ratio of GMTs and GMRs between two groups and the corresponding CI will be estimated additionally.

The total IgG (as measured by ECL) against serogroups A, C, W and Y at baseline (Day 1, Month 0) and

- at 1 month after the first (Day 31, Month 1) and the last vaccination (Day 211, Month 7) for the ABCWY group (pooled lots), and
- at 1 month after the MenACWY vaccination in the ACWY group (Day 31, Month 1),

will be analyzed in a comparable way as described above for hSBA titres. Since total IgG is measured as concentration instead of titer, the resulting geometric mean of the concentrations is abbreviated as GMC.

**Table 7 LLOQ and ULOQ of total IgG (as measured by ECL) MenACWY indicator strains**

Strain	LLOQ	ULOQ
Men A	CCI	
Men C		
Men W		
Men Y		

For each *N. meningitidis* A, C, W and Y and for each (individual response) and all (composite response) serogroup B indicator strain (M14459, M13520, 96217 and NZ98/254) the percentages of subjects with hSBA titres  $\geq$ LLOQ and of subjects with 4-fold rise and the corresponding exact 2-sided 95% CIs based on Clopper-Pearson method will be calculated for each study group at each timepoint not previously analyzed. Ninety-five percent (95%) CIs for the difference in percentages between ABCWY (pooled lots) on the one hand and MenB\_0\_2\_6, MenB\_0\_6, and ACWY groups, respectively, on the other hand, will be constructed using the method of Miettinen and Nurminen [[Miettinen](#), 1985].

For each *N. meningitidis* serogroup A, C, W and Y, analyses of hSBA GMTs, percentages of subjects with hSBA titres  $\geq$ LLOQ and of subjects with 4-fold rise, will be repeated by subjects with and without a previous MenACWY vaccination (primed and unprimed). Similarly, analyses of GMCs of the total IgG (as measured by ECL) against serogroups A, C, W and Y will be repeated by subjects with and without a previous MenACWY vaccination (primed and unprimed).

#### 5.4.1.5. Cohen kappa level of agreement

The human serum bactericidal assay (hSBA) and the endogenous complement human serum bactericidal assay (enc-hSBA) provide two different types of results for B strains; the hSBA gives a quantitative, continuous result (hSBA titer) while the enc-hSBA gives a qualitative, categorical result (with/without bactericidal activity).

To assess the agreement between hSBA and enc-hSBA, the Kappa statistics [[Cohen, 1960](#)] will be used and the hSBA results will be categorized as follows:

- The hSBA will be categorized as  $<$ LLOQ and  $\geq$ LLOQ (Ref. [Table 6](#)). Agreement will be assessed versus the positive and negative categories of the enc-hSBA at 1:4 dilution.

To evaluate the strength of the agreement, the following scale [[Landis, 1977](#)] will be used:

**Table 8 Strength of agreement scale**

Kappa	Strength of Agreement
< 0.00	Poor
0.00-0.20	Slight
0.21-0.40	Fair
0.41-0.60	Moderate
0.61-0.80	Substantial
0.81-1.00	Almost Perfect

A 95% Confidence Interval (CI) will be provided together with the point estimate of the Kappa for each of the above situations. The McNemar test will be also performed using the same categorizations of the hSBA results as described above. The aforementioned comparisons/tests will be all performed overall across vaccine groups, separately for each serogroup B test strain. The following SAS code will be used for the Kappa calculation and the McNemar test:

```
PROC FREQ data=dataset;
table assay1_res*assay2_res / agree;
run;
```

where assay1\_res represents the enc-hSBA result, assay2\_res represents the precategorized hSBA result.

## 5.4.2. Additional considerations

### 5.4.2.1. Immunological non-inferiority: MenABCWY vs. rMenB+OMV NZ

As a sensitivity analysis, a parametric model will be run. A generalized linear model with factors for vaccine group and randomization factors (i.e. region (US/ex-US), age category (10-17 YoA/18-25 YoA), previous MenACWY vaccination (y/n)) will be ran, with the Binary distribution and link function is identity, and outcome is 4-fold rise. If the lower limit of the two-sided 95% CI for the difference in percentage of subjects with 4-fold rise between the 2 groups (ABCWY (pooled) lots –MenB) coming from the model is above -10%, also the sensitivity analysis has demonstrated non-inferiority.

### 5.4.2.2. Effectiveness by each of the endemic US N. meningitidis serogroup B strains

The SAS code to analyse the Vaccine effectiveness (Test-based): rMenB+OMV NZ - 3 doses (0,2,6-months schedule) by strain is specified below. Treatment, and randomization factors (i.e. region (US/ex-US), age category (10-17 YoA/18-25 YoA), previous MenACWY vaccination (y/n)) will be modelled as fixed effect. To account for a possible over-dispersion, the DSCALE option in the model statement will be evaluated first. The DSCALE will be kept in the model only if the F-statistics for the DSCALE parameter is significant ( $p < 0.05$ ). The following SAS code will be used for the VE calculation:

```

ods trace on;
ods output GEEEmpPEst = genmod_stats
CONVERGENCESTATUS = converge ;

PROC GENMOD data=dataset descending;
class trtgrp region agecat previousACWY;
by strain ;
model outcome = trtgrp region agecat previousACWY / dist= bin link= log
DSCALE alpha=0.05;
estimate 'MenB026-ACWY' trtgrp 1 0 0 0 0 -1/ alpha= 0.05 exp;

/*trtgrp R is MenB0,2,6 and trtgrp W is ACWY*/

run;

ods output close;

data genmod_stats;
set genmod_stats;
by strain ;
where parm = 'trtgrp' and level1 = '1';
rr = exp(estimate);
ub = exp(uppercl);
ve = (1 - rr)*100 ;
ve_ll = (1 - ub) * 100 ;
if ve_ll > 65 then success = 1 ;
else success = 0 ;
run;

```

where outcome represents the Bernoulli distributed outcome without bactericidal activity at a 1:4 dilution (i.e. response is 1 if titre < 4, and 0 if titre  $\geq$  4), one month after the 3rd vaccination in MenB0,2,6 and one month after the MenACWY vaccination for the ACWY arm, trtgrp indicates the vaccine groups, strain is the serogroup B strain variable, region is either US or ex-US, agecat is the age at enrolment (10-17 YoA or 18-25 YoA), and previousACWY is previous ACWY vaccination (y/n) at enrolment.

rr is the relative risk (RR), which is obtained from the estimated parameters from PROC GENMOD. Vaccine effectiveness (VE) is then derived as (1-rr)x100%.

ub represents the upper bound of the 95% CI of the relative risk. ve\_ll is the lower bound of the 95% CI for VE, if the value is greater than 65%, then the Vaccine effectiveness (Test-based): rMenB+OMV NZ - 3 doses (0,2,6-months schedule) objective is successful.

In summary in case of convergence issue the following hierarchical decision tree will be applied

- Binary model including region, agecat, and previousACWY
- Binary model, excluding region, agecat, and previousACWY
- Cochran-Mantel-Haenszel (CMH) method (if strain has 100% killed or 0% killed for ANY treatment)
- VE set to 0% (if strain has 100% killed for both treatment)

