**5.4.1.2. Effectiveness by each of the endemic US *N. meningitidis* serogroup B strains**

Analysis set: FAS will be the primary analysis population. The ABCWY (pooled lots) group and the MenB group comparator that will be selected (ref: the footnote of [Figure 2](#)) will be used for the purpose of this analysis.

Statistical method: The VE per strain will be calculated as described in Section [5.3.1.1](#), using a generalised linear model with vaccine group, and randomization factors (i.e. region (US/ex-US), age category (10-17 YoA/18-25 YoA), previous MenACWY vaccination (y/n)) as independent variables, and alpha=0.05 leading to 95% CI. In case for a strain 100% response will be observed in both vaccine groups, VE against these strain will be assessed by calculating 95% CI for relative risk from raw proportions, and VE=1-RR.

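### SAP 5.4.2.2: the per-strain VE model applies DSCALE to single 0/1 results under a retention test that does not exist, so the 95% limits can have the wrong width

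*SAP*

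**What the plan says.** SAP 5.4.2.2 runs PROC GENMOD separately for each strain with "model outcome = trtgrp region agecat previousACWY / dist= bin link= log". The response is defined in the text: "where outcome represents the Bernoulli distributed outcome without bactericidal activity at a 1:4 dilution". There is no REPEATED statement, so each subject contributes one record per strain and the limits are model-based.

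On the scale, the text says "To account for a possible over-dispersion, the DSCALE option in the model statement will be evaluated first", and then "The DSCALE will be kept in the model only if the F-statistics for the DSCALE parameter is significant", at p<0.05. The code that is to be used carries "DSCALE alpha=0.05" with no condition attached. Section 5.4.1.2 sets the level for this analysis: "alpha=0.05 leading to 95% CI".

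The only contrast printed is "estimate 'MenB026-ACWY' trtgrp 1 0 0 0 0 -1/ alpha= 0.05 exp". The code then reads its results from the GEEEmpPEst table and sets a success flag when the lower VE limit exceeds 65. The closing text says that ve_ll "is the lower bound of the 95% CI for VE, if the value is greater than 65%, then the Vaccine effectiveness (Test-based" objective for the 0,2,6-months schedule counts as successful.

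The same DSCALE wording stands in 5.3.2.1 for the primary VE model, and in the earlier SAP amendments bound in the same file.

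**The concern.** A single Bernoulli result has variance p(1-p), fixed by its mean. With one record per subject per strain, no extra-binomial variation can be estimated. Deviance/df on such data is a function of the fitted probabilities alone: well below 1 when nearly all sera kill, and above 1 when about half do. DSCALE multiplies every model-based standard error by the square root of that quantity, so the interval width would follow the kill rate for a reason unrelated to precision.

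The stated safeguard cannot be carried out. The scale is deviance/df, and the procedure gives no F-test for it; the F-statistics printed when a scale is estimated concern the model effects. A programmer must therefore either follow the code, which has DSCALE in, or invent a rule. Nothing in the SAP groups the records or restricts the scale to values of at least 1.

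At stake are the confidence limits of a stated secondary objective across the 110-strain panel.

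**Working it through.** **The plan's own counts.** Section 3.3 assumes 25% dropout: 912 × 0.75 = 684, 548 × 0.75 = 411, 183 × 0.75 = 137.25, and 2 × 912 + 3 × 548 + 183 = 3651. These agree with the SAP.

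**Results per strain.** The glossary gives about 35 of 110 strains per subject. So 684 × 35/110 ≈ 218 for each MenB group, 411 × 35/110 ≈ 131 for each ABCWY group and 137 × 35/110 ≈ 44 for ACWY. The total is 873, of which 829 are in vaccine groups.

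**Formulae.** Expected deviance per 0/1 record is D(p) = -2[p ln p + (1-p) ln(1-p)]. The scale is φ = ΣnD(p)/df, the SE multiplier is √φ, and the approximate coverage is 2Φ(1.96√φ) - 1.

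**One case in full** (assumed: 90% unkilled in ACWY, 2% in all vaccine groups, six groups as coded). D(0.02) = 0.196 and D(0.90) = 0.650. φ = (829 × 0.196 + 44 × 0.650)/(873 - 6) = 0.22, and √φ = 0.47. Approximate coverage is 2Φ(0.92) - 1 ≈ 64%; simulation gives 66%.

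For the VE limit, the unscaled SE of log RR for one MenB group is √[0.98/(218 × 0.02) + 0.10/(44 × 0.90)] = 0.477. With ln(0.02/0.90) = -3.807, the lower VE limit is 1 - exp(-3.807 + 1.96 × 0.477) = 94.3%. With the SE multiplied by 0.47 it is 96.6%.

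**Range over assumed vaccinee rates** (ACWY 90% unkilled, six-group fit; coverage from 20,000 simulated treatment-only fits with no true over- or under-dispersion):

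| Unkilled, vaccinees | φ | SE multiplier | Coverage with DSCALE | Coverage, scale 1 | Lower VE limit, scale 1 → DSCALE |
|---|---|---|---|---|---|
| 2% | 0.22 | 0.47 | 66.0% | 96.6% | 94.3 → 96.6 |
| 5% | 0.41 | 0.64 | 78.8% | 95.9% | 90.0 → 91.9 |
| 10% | 0.66 | 0.81 | 88.5% | 95.2% | 83.3 → 84.5 |
| 20% | 0.99 | 1.00 | 95.3% | 95.7% | 70.5 → 70.5 |
| 30% | 1.20 | 1.10 | 97.0% | 95.0% | 58.2 → 57.3 |
| 50% | 1.36 | 1.17 | 97.8% | 95.0% | 34.5 → 32.6 |

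**Other assumptions.** With ACWY between 60% and 95% unkilled, the SE at 2-5% unkilled in vaccinees is 1.5 to 2.2 times too small in the six-group fit and 1.3 to 2.1 times in a two-group fit. At 85% in ACWY, φ is 0.23 at 2% and 0.42 at 5%, with coverage about 65% and 80%. Full fits with the three covariates (ACWY 85%) gave φ of 0.42, 0.66 and 1.32 at 5%, 10% and 40% unkilled.

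**The 65% flag.** In the table's cases with VE near 90% or higher, both lower limits are far above 65, so the flag does not change. At a true VE of exactly 65% (six-group fit), it fires in 8.2% instead of 2.5% of simulations if only 20% of ACWY results are unkilled, 5.5% instead of 2.7% at 30%, and near or below nominal at 50% or more.

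**The results table.** GEEEmpPEst is a GEE output. Without a REPEATED statement it is not produced, so the data step that follows has nothing to read.

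**The case against.** The strongest reply is that the text makes DSCALE conditional and gives its purpose as over-dispersion. Read as a one-sided test of scale above 1, the rule would drop DSCALE for well-covered strains, where deviance/df is below 1. The too-narrow limits would then never arise, and only somewhat wide limits for strains with about 30-50% unkilled would remain. That stands as one reading. It does not rescue the rule, which names a statistic that does not exist, while the code keeps DSCALE in.

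Several further points stand:

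- The kill rates are assumed.
- Section 5.4.1.2 names pooled ABCWY and the selected MenB comparator on the FAS, whereas the code has six groups, so the group mix is open. This is why both fits are given.
- The fallback list at the end of 5.4.2.2 sends a strain to the Cochran-Mantel-Haenszel method if any group has 0% or 100% killed. With the counts above, at least one vaccine group would be 100% killed for about 69% of strains at 1% unkilled and about 22% at 2%. So many of the most extreme cases leave the DSCALE model; at 5% or more this gives no relief.
- Per-strain VE is a secondary objective worded as an assessment, and it is not among the hypotheses tested hierarchically in Section 6.
- The missing GEEEmpPEst table would show itself when the program is run, so it cannot silently bias a limit.

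**Conclusion.** The plan is wrong as written. The scale correction has no basis for single 0/1 results, the test that should govern it does not exist, and text and code disagree. If DSCALE stays in as coded, and under the assumed rates above, log-RR standard errors are about 1.3 to 2.2 times too small at 2-5% unkilled in vaccinees and about 1.1 to 1.2 times too large at 30-50%.

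A reader might infer three stronger things that the SAP does not support.

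- That well-covered strains will certainly receive limits up to twice too narrow. This depends on how the rule is read and on kill rates the SAP does not give. Nor is twice a ceiling: at 1% unkilled the factor is about 2.7 in the six-group fit, though many such strains would move to the fallback method.
- That conclusions on strains with high VE would change. The lower limit moves by about 1 to 2 points and stays far above 65, so the harm there is overstated precision.
- That the primary VE result is affected. The model in 5.3.2.1 takes its limits from the empirical GEE output, which does not depend on the scale.

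The sentence declaring the primary 0,2,6 objective successful on a single-strain 95% limit contradicts 5.3.1.1, which uses a 97.5% interval over the whole panel. Section 6 uses no strain-level flag, so this is a drafting fault, but it should go.

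**What to change.** In 5.4.2.2:

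- Delete DSCALE and the F-test rule, and state that the scale is fixed at 1. Simulated coverage is then 95-97% at all the assumed rates.
- Take VE and its 95% CI from ESTIMATE output, with one statement for each rMenB+OMV NZ schedule and one for pooled ABCWY, each against ACWY. The single contrast now printed does not cover the endpoint, and the GEEEmpPEst table will not exist.
- Remove the by-strain success flag and the sentence tying it to the primary objective.

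In 5.3.2.1, deleting DSCALE is tidying only and leaves the empirical GEE limits unchanged.

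The cost is deleted text, one model option and a few added ESTIMATE statements, with no change to design or data. Compared with the printed code, limits become wider for well-covered strains and slightly narrower for strains with about 30-50% unkilled.

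### By-strain VE is set to 0% for a strain that every vaccine and ACWY serum kills, although VE is then 0/0 and not estimable, and the neighbouring rules do not settle the case

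*SAP*

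**What the plan says.** All references are to the current SAP text (Amendment 9).

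- **Event and formula.** Section 5.4.2.2 states that "outcome represents the Bernoulli distributed outcome without bactericidal activity at a 1:4 dilution (i.e. response is 1 if titre < 4", and that "Vaccine effectiveness (VE) is then derived as (1-rr)x100" percent. Section 5.3.1.1 defines RR as the share of samples without activity in the vaccine group over the same share in the ACWY group. Table 1 confirms ACWY at Month 1 as the comparator for by-strain VE.
- **Section 5.4.1.2, special rule.** "In case for a strain 100% response will be observed in both vaccine groups", then "VE against these strain will be assessed by calculating 95% CI for relative risk from raw proportions, and VE=1-RR".
- **Section 5.4.2.2, fallback list.** It is introduced by "In summary in case of convergence issue the following hierarchical decision tree will be applied". After two model steps come "Cochran-Mantel-Haenszel (CMH) method (if strain has 100% killed or 0% killed for ANY treatment" and, last, "VE set to 0% (if strain has 100% killed for both treatment".

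Neither section refers to the other. No interval is given for the 0% value, and neither section provides for a result of not estimable.

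**The concern.** A strain killed by every serum in both compared groups gives no information on relative reduction, because the control group has no unkilled serum to reduce. Writing 0% turns an absent estimate into a statement of no effect. In a by-strain table, a strain that every serum kills would then stand beside strains on which the vaccine has no effect.

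The surrounding text does not resolve this. The CMH condition says any treatment, which includes both, so two steps of one list claim the same strain. The wording in Section 5.4.1.2 leaves open what a response is and which two groups are meant. What is printed for such a strain would depend on which sentence the programmer follows. By-strain VE is a stated secondary objective in Table 1.

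**Working it through.** **Inputs.** Evaluable subjects (Section 3.3): 684 per MenB group, 411 per ABCWY lot, 137 ACWY. These reproduce from 25% dropout: 912 × 0.75 = 684; 548 × 0.75 = 411; 183 × 0.75 = 137.25. Strains per subject (Section 10.3): about 35 of 110. Illustrative sera per strain:

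- MenB: 684 × 35/110 = 217.6, about 218
- Pooled ABCWY: 3 × 411 × 35/110 = 392.3, about 392
- ACWY: 137 × 35/110 = 43.6, about 44

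**Step 1: does the plan's 0% follow from its own formula?** With all sera killed there are no events in either group.

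- Raw: RR = (0/218) / (0/44) = 0/0, so RR, VE and the interval are undefined.
- Mantel-Haenszel over strata k: RR = Σ(a_k·n0_k/N_k) / Σ(c_k·n1_k/N_k), where a_k and c_k are the unkilled counts in the vaccine and ACWY groups. All are 0, so this is again 0/0.

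The stated 0% is not reproduced by either route.

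**Step 2: what do the data say about VE here?** Add 0.5 to each event count and 1 to each denominator, with SE(log RR) = √(1/a − 1/n1 + 1/c − 1/n0) on the adjusted counts.

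- MenB: RR = (0.5/219)/(0.5/45) = 0.205, VE 79.5%, 95% CI −922% to 99.6%
- Pooled ABCWY: RR = (0.5/393)/(0.5/45) = 0.115, VE 88.5%, 95% CI −470% to 99.8%

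The point estimate reflects only the ratio of group sizes, and the interval is uninformative. What can be estimated is the share killed. The Clopper-Pearson 95% lower limit is 0.025^(1/218) = 98.3% for 218/218 and 0.025^(1/44) = 92.0% for 44/44.

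**Step 3: the neighbouring result.** With one unkilled ACWY serum, RR = (0/218)/(1/44) = 0 and VE = 100%. The listed value moves from 0% to 100% on one control serum.

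**Step 4: readings of the Section 5.4.1.2 rule.**

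| Reading of 100% response in both vaccine groups | What that rule gives | Relation to the 0% step |
|---|---|---|
| Killed, vaccine and ACWY | Raw RR = 0/0 | Same strain; the rules conflict |
| Coded response = 1 (not killed), vaccine and ACWY | RR = 1/1 = 1, VE 0% | Opposite strain; no collision, but both are listed as 0% |
| Killed, ABCWY and selected MenB group | RR = 0, VE 100%, if any ACWY serum is unkilled | The 0% step does not apply if its pair is vaccine and ACWY; CMH does |

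On the second reading VE 0% is a proper estimate. A Wald log-RR interval has zero width there, but a score interval does not. With z² = 3.84, the RR limits are 218/(218 + 3.84) = 0.983 and (44 + 3.84)/44 = 1.087, so VE runs from about −8.7% to 1.7%.

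**Step 5: how often?** The case requires at least that all ACWY sera kill. For background killing q, taking sera as independent, that has probability q^44: 0.90 gives 1.0%, 0.95 gives 10%, 0.99 gives 64%. These q values are assumptions; the SAP gives none.

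**The case against.** The strongest reply has four parts.

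1. **The two rules may not collide.** If response follows the model coding, Section 5.4.1.2 is about a strain that no serum kills, and its VE of 0% is correct. This stands. A reader might infer that the SAP certainly gives two contradictory rules for one strain, but the text supports that on only one reading. The ambiguity is certain; the conflict is not.
2. **The list is hierarchical.** Zero could be meant as a terminal value once everything else fails. That is coherent, but it is not written, and Section 5.4.1.2 does not defer to the list. Even as a last resort, 0% is a value the formula cannot give.
3. **Zero is conservative.** It can be read as no reduction beyond control, and it cannot create a false success. Both remarks are fair. They limit the harm but do not make the number an estimate: the interval in Step 2 excludes almost nothing.
4. **The damage is easily exaggerated.** A reader might infer that the same data could be published as 0% or 100%, or that the error reaches 100 percentage points. The first needs the 0% step to mean MenB and ABCWY, whereas the code beside it contrasts MenB 0,2,6 with ACWY. The second needs a true VE to measure against, and here none can be estimated. The 98.3% lower limit concerns percent killed, not VE.

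**Conclusion.** The 0% rule in Section 5.4.2.2 is wrong as written: for a strain killed by every serum in both compared groups, VE is not estimable. This follows from the SAP's own event coding and VE formula and does not depend on the illustrative sample sizes. The CMH step overlaps with it and fails in the same way. Section 5.4.1.2 is ambiguous: it either conflicts with the 0% rule or leaves always-killed and never-killed strains under the same 0% label.

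The reach is limited to secondary by-strain VE, and the case is probably rare, though the SAP gives no background killing rate to confirm that. The primary test-based VE, its 65% criterion and the alpha hierarchy of Section 6 do not use these rules. The change is worth making because it is cheap and corrects what would be printed for a stated secondary objective.

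**What to change.** 1. In Section 5.4.2.2, replace the 0% step with: if no serum is unkilled in either the vaccine group or the ACWY group, RR and VE are reported as not estimable, with n/N killed per group and Clopper-Pearson 95% CIs.
2. Restrict the CMH step to strains where only one of the two compared groups is at 0% or 100% killed. State separately where a strain killed by all vaccine sera and no ACWY serum goes; RR is 0 there and computable.
3. Reword the Section 5.4.1.2 rule as killed or not killed, vaccine group versus ACWY group. Keep it for strains that no serum in either group kills: RR = 1 and VE 0% from raw proportions, with a named interval that does not collapse, such as a score interval. Do not delete this rule, since item 1 does not cover those strains.

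The cost is a few sentences of SAP text and a small change to the by-strain program. The downside is that a few strains show not estimable instead of a number.
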